Study Protocol and Statistical Analysis Plan

Investigating Hearing Aid Frequency Response Curves - ID# 12792

July 24, 2024

NCT05828017

Investigating Hearing Aid Frequency Response Curves - ID# 12792

1 Objectives and hypotheses of the clinical investigation

1.1 Purpose of the clinical investigation claims for clinical performance, effectiveness or safety of the investigational device that are to be verified

This exploratory study evaluates a series of proposed frequency gain curves, comparing them to our current frequency gain curve across various hearing aid programs and configurations (both acoustic and streaming). Participants were asked to rate speech clarity, noise intrusion, comfort, and overall preference in the presence of live stimuli. Additionally, they were asked to rank two proposed streaming frequency response curves alongside our current standard streaming curve. SRT50 scores were also collected using the US Matrix test task. The aim of this clinical investigation is to assess whether the proposed gain offsets provide benefits for hearing aid users in different listening environments.

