1.3 Secondary Objectives

One secondary objective of this study was to assess whether two newly proposed streaming frequency response curves (Variation #2 and Variation #3) are preferred by hearing aid users compared to our current streaming frequency response curve, across various musical genres and speech stimuli.

Another secondary objective was to evaluate the impact of the proposed frequency response curve (Variation #1) on speech performance in noise, specifically by comparing SRT50 scores to those obtained with the current frequency response curve. Participants will complete a standardized test (OLSA – US Matrix test) in noise within a sound booth, under three conditions: a program with the proposed frequency response curve, a program with the current frequency response curve, and an unaided condition (without hearing aids).

2 Design of the clinical investigation

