2.1 General

2.1.1 Design Type

This clinical investigation was an interventional study conducted at two investigation sites. The study involved a single group of participants who were tested under all conditions in a crossover design. During the live preference ratings, participants were blinded to the program they were using, although the investigator was aware of the program, as they programmed the hearing aids prior to testing. For the streaming sound quality task, participants wore headphones, and both participants and investigators were blinded to the program being rated.

The table below indicates the various programs that each participant evaluated.

Programs	Interventions
Acoustic Programs	
Program 1	Standard Frequency Response Curve
Program 1	Proposed Frequency Response Curve - Variation #1
Program 2	Standard Frequency Response Curve
Program 2	Proposed Frequency Response Curve - Variation #1
Program 3	Standard Frequency Response Curve
Program 3	Proposed Frequency Response Curve - Variation #1
Program 4	Standard Frequency Response Curve
Program 4	Proposed Frequency Response Curve - Variation #1
Streaming Programs	
Program 5	Current Streaming Frequency Response Curve – Variation #2
Program 5	Proposed Streaming Frequency Response Curve - Variation #3
Program 5	Proposed Streaming Frequency Response Curve - Variation #4
US Matrix Test Task Programs	
Program 1	Standard Frequency Response Curve
Program 1	Proposed Frequency Response Curve - Variation #1
Unaided	No hearing devices

Acoustic Task:

Participants were seated in the center of a 12-loudspeaker array, positioned at azimuths of 0°, 30°, 60°, 90°, 120°, 150°, 180°, 210°, 240°, 270°, 300°, and 330° in a sound-treated room. The 12 speakers were used to render ambisonic audio scenes. While immersed in these scenes, participants were asked to toggle between two frequency response curves: the standard curve and the proposed frequency response curve – Variation #1 – using an iPhone.

Participants were then asked to rate the following attributes for each program:

1. Which program resulted in increased noise intrusion?
2. Which program provided better speech clarity?
3. Which program offered greater comfort?
4. Which program did they prefer overall?

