2.2 Determination of Sample Size

Our previous study (ID – 3167, NCT05521308) evaluated similar hearing aids programs (e.g., the current program vs. the proposed programs) and had a similar study design. Therefore, we have determined that a sample size of 20-25 participants, which is the sample we used for the previous study - ASQ study (SRF-3167), is sufficient for our purposes.

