2.4.3 Secondary Endpoint Analysis

The secondary analysis focused on the subjective sound quality ratings provided by participants during the streaming task. Participants were asked to rank three stimuli in order of overall preference and sound quality, with each stimulus corresponding to one of the three frequency response curves being tested (Variations #2, #3, or #4). The analysis involved calculating the mean number of times each curve was ranked as the highest, lowest, and middle choice across all stimuli.

The analysis proceeded as follows:

1. **Chi-Square Analysis (First Step):** A chi-square test was conducted at each ranking level (highest, middle, and lowest) to determine how each frequency response variation was ranked.
2. **Chi-Square Analysis (Second Step):** Two additional chi-square tests were run at each ranking level to compare how the proposed frequency response curves (Variations #3 and #4) were ranked against Variation #1.

In total, 9 chi-square analyses were performed for this task.

For the speech-in-noise tests, the average SRT50 scores across all participants were compared to determine equivalence. Lower SRT50 scores indicate better performance.

1. **One-Way ANOVA:** A one-way ANOVA was conducted to assess the impact of the different interventions (standard curve, Variation #1, and unaided) on the SRT50 scores.
2. **Post-Hoc Analyses:** Post-hoc pairwise comparisons were conducted following the ANOVA, where one intervention was excluded at a time to assess differences between the remaining interventions.

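### SRT50 is analysed with difference tests alone and no margin, so the stated aim of determining equivalence cannot be met

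*Combined protocol and SAP*

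**What the plan says.** Section 2.4.3 (Secondary Endpoint Analysis) gives the aim of the speech-in-noise analysis: "For the speech-in-noise tests, the average SRT50 scores across all participants were compared to determine equivalence". It adds the direction of the score, "Lower SRT50 scores indicate better performance", and lists two steps:

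1. "A one-way ANOVA was conducted to assess the impact of the different interventions (standard curve, Variation #1, and unaided) on the SRT50 scores"
2. "Post-hoc pairwise comparisons were conducted following the ANOVA, where one intervention was excluded at a time to assess differences between the remaining interventions"

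Section 1.3 sets a more modest objective, which is to "evaluate the impact of the proposed frequency response curve (Variation #1) on speech performance in noise" by comparing SRT50 with the current curve. It does not mention equivalence.

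On design, section 2.1.1 says: "The study involved a single group of participants who were tested under all conditions in a crossover design". On size, section 2.2 says "we have determined that a sample size of 20-25 participants" is sufficient, citing only the size of a previous study. No margin in dB SNR, significance level, confidence level or equivalence decision rule is given in any section.

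**The concern.** The aim and the tests do not match. The ANOVA and the pairwise comparisons can produce evidence that conditions differ. They cannot produce evidence that two conditions are close enough to be treated as the same, because closeness is never defined. The document does not say that a non-significant result will be read as equivalence, but it offers no other route to that conclusion.

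The report could therefore state that Variation #1 leaves speech understanding in noise unchanged when the data cannot exclude a loss. SRT50 is the study's only objective speech-in-noise outcome, so nothing else in the plan would correct such a statement.

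**Working it through.** **1. What each step tests.**

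| Step in 2.4.3 | Null hypothesis | What a non-significant result shows |
|---|---|---|
| One-way ANOVA, three conditions | All three means equal | No difference detected |
| Pairwise comparison, Variation #1 vs standard | The two means equal | No difference detected |
| Needed for equivalence (not in the plan) | True difference at or beyond ±margin | Equivalence not shown; rejection shows it |

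The mismatch follows from this table and needs no assumed number.

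**2. The omnibus ANOVA does not isolate the aided comparison.** It includes the unaided condition. In simulation with the two aided curves truly equal, unaided 3 dB worse, between-person SD 2.5 dB, within-person SD 1.0 dB and n = 20 (all but n assumed), it rejects in about 99.8% of runs. That rejection says nothing about Variation #1 against the standard curve.

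**3. Inputs for the illustration.** From the document: 20 to 25 participants (section 2.2), 20 analysed in the acoustic task (section 2.4.2), and every participant tested in every condition (section 2.1.1). The document gives no SD, correlation, margin or significance level, and its sample size rests on no formula, so there is no stated figure to reproduce. Assumed: between-person SD of SRT50 1.5, 2 or 3 dB; within-person correlation r of 0.5, 0.7 or 0.9; true worsening 1 dB; two-sided 5% test.

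**4. Chance that a paired test misses a true 1 dB worsening.**

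SD of the paired difference: SD_d = SD × √(2(1 − r)). For SD 2 and r 0.7: 2 × √0.6 = 1.55 dB.

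The paired t statistic has noncentrality √n × 1/SD_d. Here that is √20/1.55 = 2.89 on 19 df, with critical value 2.093. The probability of a non-significant result is 0.218.

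All cases, for SD 1.5 / 2 / 3 dB:

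| r | SD_d (dB) | 90% CI half-width, n = 20 (dB) | Missed, n = 20 | Missed, n = 25 |
|---|---|---|---|---|
| 0.5 | 1.50 / 2.00 / 3.00 | 0.58 / 0.77 / 1.16 | 19% / 44% / 71% | 11% / 33% / 64% |
| 0.7 | 1.16 / 1.55 / 2.32 | 0.45 / 0.60 / 0.90 | 5% / 22% / 55% | 2% / 13% / 46% |
| 0.9 | 0.67 / 0.89 / 1.34 | 0.26 / 0.35 / 0.52 | 0% / 0.3% / 11% | 0% / 0% / 5% |

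Section 2.4.3 does not say whether the ANOVA uses the pairing. If the pairwise tests ignore it (38 df, simulated at r = 0.7, n = 20), the miss rates are about 43% / 76% / 94%.

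**5. One result read both ways.** Take SD_d = 2.0 dB and n = 20, and suppose the observed worsening is 0.8 dB (illustrative). The 95% half-width is 2.093 × 2.0/√20 = 0.94, so the 95% interval is −0.14 to 1.74 dB and the test is non-significant. The 90% interval is 0.8 ± 0.77, or 0.03 to 1.57 dB, which does not exclude a 1 dB loss. The plan's test finds no difference; an equivalence rule with a 1 dB margin would call the result inconclusive.

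**6. The same data under an equivalence rule.** Two one-sided 5% tests (TOST), which is the same as requiring the 90% CI to lie inside ±margin; n = 20, simulated, SD 1.5 / 2 / 3 dB:

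| r | 1 dB margin, true difference 0: equivalence shown | 1.5 dB margin, true worsening 1 dB: equivalence shown |
|---|---|---|
| 0.5 | 78% / 40% / 3% | 42% / 28% / 15% |
| 0.7 | 96% / 74% / 20% | 58% / 40% / 23% |
| 0.9 | 100% / 100% / 88% | 94% / 78% / 49% |

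With a 1 dB margin and a true 1 dB worsening, equivalence is declared at most about 5% of the time in every case. That limit holds only for a true difference at or beyond the chosen margin. The last column shows that a 1 dB loss is often accepted under a 1.5 dB margin, which is tolerable only if 1.5 dB is the real limit.

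**The case against.** The strongest reply is that the case rests on one word. Equivalence appears once, in the sentence introducing the SRT50 analysis, and not in the purpose, the objectives or the design. The objective asks for impact and the two listed steps assess impact and differences, so they agree with each other. The word may be loose shorthand for checking whether scores are the same or different. The harm is also conditional: if the comparison is significant, or the report states only the estimated difference, no false claim arises. The SDs, correlations and 1 dB worsening all come from outside the document. The study describes itself in these terms: "This exploratory study evaluates a series of proposed frequency gain curves".

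Much of this stands. The loose reading is plausible, and if it is right the repair is mainly one of wording. The percentages illustrate the logic and do not measure this study's risk. The pairing question is separate and adds no weight to the equivalence point. What does not stand is leaving the text alone. The published plan names a conclusion, gives no rule for reaching it, and leaves a non-significant p-value as the only available basis.

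**Conclusion.** The concern holds. Section 2.4.3 sets out to determine equivalence using methods that can only detect differences, and no section supplies a margin or interval rule. This is an error in the plan as written, not merely a missing detail, and it should be fixed.

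The logical point depends on no assumption. The size does: with 20 participants and the assumed ranges, a true 1 dB loss would go undetected in 0% to 71% of studies with a paired test, so the risk runs from negligible to large. The reach is limited to one secondary endpoint. The primary preference result is untouched.

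**What to change.** Compute each participant's SRT50 difference, Variation #1 minus standard, and report the mean with its confidence interval. Then take one of two routes.

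- **Drop the equivalence wording.** State that the analysis estimates the difference in SRT50 between the curves, with its interval. This matches section 1.3 and needs no margin. It costs one wording change and one paired interval, and is the simpler choice.
- **Keep equivalence and define it.** Specify a justified margin in dB SNR and claim equivalence only if the 90% CI of the paired difference lies wholly inside it (paired TOST at 5%); otherwise report the result as inconclusive. Section 2.4 is written in the past tense, so a margin set after the results were seen must be disclosed as post hoc, which weakens error control. Equivalence also becomes harder to claim: with a 1 dB margin and truly equal curves, 20 participants confirm it between 3% and 100% of the time over the assumed ranges.

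Under either route, report aided versus unaided as a separate difference comparison. No new data are needed.

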The responses were tallied for further analysis. This process was repeated for four different hearing aid programs, where the frequency response curves were compared but not the programs themselves. In other words, ratings from one hearing aid program were not compared with those from another.

Streaming Task:

Participants were asked to wear headphones while listening to three versions of the same pre-recorded stimulus: the Current Streaming Frequency Response Curve (Variation #2), the Proposed Streaming Frequency Response Curve (Variation #3), and the Proposed Streaming Frequency Response Curve (Variation #4). This process was repeated with multiple different stimuli. After listening to each version for each stimulus, participants were asked to rank them from most preferred to least preferred, with one version ranked in between. Responses were recorded on a laptop, and the rankings for each curve were tallied and compared at the end for further analysis.

US Matrix Test Task:

Participants were seated at the center of an 8-loudspeaker array positioned at azimuths of 0°, 45°, 90°, 135°, 180°, 225°, 270°, and 315° within a sound-treated room. Noise was presented from all speakers, except the one at 0° azimuth, while speech was presented from the front speaker at 0°. Participants were asked to repeat sentences they heard while wearing hearing aids programmed with either the Standard Frequency Response Curve or the Proposed Frequency Response Curve – Variation #1, or while wearing no hearing aids at all. A total of 20 sentences were presented for each condition. At the end of the experiment, a dB SNR (signal-to-noise ratio) score was calculated for each condition and used for further analysis.

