2.4.2 Primary Endpoint Analysis

The primary analysis focused on the subjective responses provided by participants during the acoustic task, comparing their experiences under different frequency response curves, hearing aid programs, and sound scenes. Scores for all 20 participants were tallied for the final analysis. Higher scores indicated a greater preference for a particular frequency response curve, while lower scores indicated a lesser preference. Additionally, the mean number of times participants preferred each frequency response curve (intervention) or rated the two interventions as equal in sound quality was calculated, based on the four sound quality attributes: comfort, noise intrusiveness, speech clarity (when applicable).

The analysis proceeded as follows:

1. **Chi-Square Analysis (First Step):** A chi-square test was conducted to compare the three means

(the mean number of times the standard curve was chosen, the mean number of times Variation #1 was chosen, and the mean number of times participants rated the sound quality as "same"). This test aimed to determine whether participants perceived a difference between the two curves by not selecting the "same" option.

2. **Chi-Square Analysis (Second Step):** Another chi-square test was conducted to compare the two means (the mean number of times the standard curve was chosen versus the mean number of times Variation #1 was chosen). This test assessed whether there was a preference between the two curves.

This process was repeated for each hearing aid program

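### SRT50 scores from a crossover are analysed with an unqualified one-way ANOVA and pairwise tests not described as paired; read ordinarily, this ignores the within-participant design and overstates the standard error

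*Combined protocol and SAP*

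**What the plan says.** Section 2.1.1 sets out the design: "The study involved a single group of participants who were tested under all conditions in a crossover design". Section 1.3 has participants complete the US Matrix test "in noise within a sound booth, under three conditions": the proposed curve, the current curve and unaided. The US Matrix task description in 2.1.1 adds that a dB SNR "score was calculated for each condition and used for further analysis". The data are therefore three continuous scores per person.

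Section 2.4.3 is the only analysis text for this endpoint. It states the aim: "the average SRT50 scores across all participants were compared to determine equivalence". It then names the omnibus test, "A one-way ANOVA was conducted to assess the impact of the different interventions" on the SRT50 scores, and describes the post-hoc comparisons as ones "where one intervention was excluded at a time to assess differences between the remaining interventions". Nothing in the document mentions a participant effect, repeated measures, within-participant differences or paired tests for SRT50. No equivalence margin or decision rule is given.

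**The concern.** Listeners with moderate to severe loss will differ from one another in speech-in-noise performance, and a listener who does poorly in one condition will probably do poorly in the others. A crossover exploits this because each person serves as their own control. An ordinary one-way ANOVA with intervention as its only factor does not. It counts differences between listeners as error, and with one intervention dropped it reduces to an unpaired two-group comparison.

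If the within-participant correlation is positive, the standard error for Variation #1 minus standard is overstated, the tests reject too rarely and power is lost. For a claim of difference the error is conservative. The stated aim, however, is equivalence, and the listed tools are difference tests. If a non-significant result is read as equivalence, the inflated error makes that conclusion easier to reach, even if Variation #1 worsens speech understanding in noise. If a confidence interval is used instead, the extra width makes equivalence harder to show. Either way, the conclusion depends on an error term that does not fit the design.

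**Working it through.** **Inputs.** Three conditions per participant (1.3 and 2.1.1). The number analysed is taken as n = 20: "Scores for all 20 participants were tallied for the final analysis" is stated in 2.4.2 for the acoustic task and is assumed here for SRT50. The planned range in 2.2 is 20-25. The documents give no SD, within-participant correlation (rho), significance level or target difference. Results are therefore in SD units, over a range of rho, at an assumed two-sided 5% level. There is no figure in the plan to reproduce.

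**Standard error of a pairwise mean difference, equal variances.**
- Treated as independent: SD × sqrt(2/n) = sqrt(2/20) = 0.316 SD.
- Paired: SD × sqrt(2(1-rho)/n). At rho 0.5 this is sqrt(2 × 0.5/20) = 0.224 SD.
- Ratio: 1/sqrt(1-rho). At rho 0.5 this is 1/sqrt(0.5) = 1.41.

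The share of precision lost, 1 minus the ratio of the true to the assumed variance, equals rho.

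**95% interval half-width.** The independent analysis uses t on 2(n-1) = 38 degrees of freedom and gives 0.64 SD whatever rho is. The paired analysis uses t on n-1 = 19.

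**Type I error and power.** Correlated normal pairs were simulated, 200,000 replicates per point. The paired detectable differences come from the noncentral t.

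| rho | SE inflation | Half-width, paired (unpaired 0.64 SD) | Actual type I error, unpaired | Power at 0.5 SD, unpaired / paired | Difference detectable with 80% power, unpaired / paired |
|---|---|---|---|---|---|
| 0.3 | 1.20 | 0.55 SD | 2.1% | 31% / 43% | 0.87 / 0.78 SD |
| 0.5 | 1.41 | 0.47 SD | 0.7% | 29% / 56% | 0.84 / 0.66 SD |
| 0.7 | 1.83 | 0.36 SD | 0.1% | 25% / 78% | 0.80 / 0.51 SD |
| 0.8 | 2.24 | 0.30 SD | 0.02% | 22% / 92% | 0.78 / 0.42 SD |

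The paired test kept its type I error at 4.9% to 5.0% throughout.

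**Omnibus test.** Three conditions with a common correlation were simulated, 100,000 replicates. The between-groups one-way ANOVA rejects a true null 1.6%, 0.4% and 0.03% of the time at rho 0.3, 0.5 and 0.7. The repeated-measures form stays between 4.9% and 5.1%.

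**If non-significance is read as equivalence.** With a true difference of 0.5 SD and rho 0.7, the unpaired test misses it in 100 - 25 = 75% of trials, the paired test in 100 - 78 = 22%.

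**Sensitivity.**
- If the unaided SD is k times the aided SD, inflation for that contrast is sqrt((1+k²)/(1+k²-2·rho·k)). With k = 2 it falls to 1.15, 1.29, 1.51 and 1.67 at rho 0.3, 0.5, 0.7 and 0.8.
- At n = 25 the detectable differences at rho 0.5 are 0.74 SD unpaired and 0.58 SD paired.
- At rho = 0 the two standard errors agree. At rho = -0.2 the independent one would be too small (ratio 0.91).

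**The case against.** The strongest objection is that the error is inferred. One-way counts factors and does not say whether the factor lies between or within participants. The authors describe the crossover themselves, so they knew the structure, and dropping one intervention at a time fits a paired comparison as well as an unpaired one. This stands to the extent that a repeated-measures analysis cannot be excluded. It does not rescue the text: a reader cannot tell which test was run, and the two can give opposite answers on the same data.

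Second, SRT50 is the second of two secondary objectives in a study that calls itself exploratory. The primary acoustic analysis is unaffected, and with positive correlation the error does not inflate false claims of difference. That limits the seriousness, although SRT50 is the only objective performance measure listed in 2.4.1.

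Third, the harmful route needs non-significance to be read as equivalence, which 2.4.3 does not say. The missing margin is also a separate defect, since a paired test without one would not show equivalence either. Both points are fair. The loss of precision remains without them.

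Fourth, the size of the effect is unknown: rho, the SD and the 0.5 SD difference are all assumed, and nothing can be expressed in dB. That is correct, and it is why a range is shown.

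**Conclusion.** The concern holds. The design yields three correlated scores per participant, and section 2.4.3 specifies an analysis that, as ordinarily read, treats them as independent. Assuming equal variances, n = 20 and rho between 0.3 and 0.8, the pairwise standard error is overstated by a factor of 1.20 to 2.24 and the nominal 5% pairwise test runs at 2.1% down to 0.02%. The direction depends on positive within-participant correlation, which is to be expected here but is not documented. Confidence is moderate because a repeated-measures analysis may have been run and loosely described. This should be fixed, in proportion to a secondary endpoint in an exploratory study.

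**What to change.** First, state in 2.4.3 whether the ANOVA and the pairwise comparisons were within-participant. If they were, naming the repeated-measures form and the paired tests is enough to settle this point.

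If they were not, replace the one-way ANOVA with a one-way repeated-measures ANOVA with a sphericity correction, or a linear mixed model with condition as a fixed effect and participant as a random effect. Replace the post-hoc step with paired within-participant contrasts. In either case, report Variation #1 minus standard with its 95% confidence interval, and base any equivalence statement on that interval against a justified margin, which the plan does not yet give, rather than on non-significance.

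The cost is a wording change and a re-run on data already collected, with no participant burden. At n = 20 the omnibus error degrees of freedom fall from 3 × 19 = 57 to 2 × 19 = 38. If rho were zero, paired power for a 0.5 SD difference would be 32.5% against 34.0% unpaired, a loss of 1.5 percentage points.

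### The SRT50 objective is one contrast, Variation #1 against the current curve, but section 2.4.3 leads with a three-condition ANOVA including unaided and leaves that contrast as one of three unranked post-hoc pairs

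*Combined protocol and SAP*

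**What the plan says.** Section 1.3 sets the second secondary objective as the effect of Variation #1 on speech performance in noise, "specifically by comparing SRT50 scores to those obtained with the current frequency response curve". The same paragraph lists unaided listening as a third test condition, but the comparison it names has only two sides.

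Section 2.1.1 makes the data within-participant: "The study involved a single group of participants who were tested under all conditions in a crossover design".

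Section 2.4.3 says that "the average SRT50 scores across all participants were compared to determine equivalence", and then gives two numbered steps. The first is "A one-way ANOVA was conducted to assess the impact of the different interventions (standard curve, Variation #1, and unaided) on the SRT50 scores". The second is "Post-hoc pairwise comparisons were conducted following the ANOVA, where one intervention was excluded at a time to assess differences between the remaining interventions". The section does not say which pair answers the objective, whether the pairwise tests are paired, whether they depend on the ANOVA result, or whether they are adjusted for multiplicity.

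**The concern.** The objective has one degree of freedom and the leading test has two. An F test over standard, Variation #1 and unaided responds to any difference among the three. In people with moderate to severe loss, the gap between aided and unaided listening may well be the largest of these. A significant result is then uninformative about the curve, although it is described as assessing the impact of the interventions.

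The comparison the sponsor wants is one of three follow-ups, and the other two compare an aided condition with unaided. A report could meet this section to the letter, lead with a significant ANOVA, and leave the curve question as one line among three, with no stated rule on which line decides. A repeated-measures ANOVA on the same three conditions would not cure this. It would correct the error term but make significance from the unaided condition more certain still.

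**Working it through.** The plan states no alpha, SD, effect size or margin for SRT50, so there is no figure of its own to reproduce. The check asks what each test responds to.

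**Inputs from the documents.** Three conditions per participant (sections 1.3 and 2.4.3). The number analysed is 20, taken from section 2.4.2: "Scores for all 20 participants were tallied for the final analysis". That sentence concerns the acoustic task, so using 20 for SRT50 is an assumption; section 2.2 gives 20-25.

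**Assumptions.** Two-sided alpha 0.05; between-participant SD (sb) 2 to 3 dB; within-participant SD (sw) 1 to 1.5 dB; unaided worse than standard by a gap of 1 to 3 dB.

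**Step 1: what drives the F when the curves are equal.** With condition means 0, 0 and G, the grand mean is G/3 and the squared deviations sum to 2G²/3. The expected between-condition mean square is sw² + (20/2)(2G²/3). The one-way error mean square is about sb² + sw², and the 5% critical value of F(2, 57) is about 3.16.

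- G = 2, SDs 3 and 1: (1 + 26.7)/(9 + 1) = 2.8, just under the critical value.
- G = 2, SDs 2 and 1: (1 + 26.7)/(4 + 1) = 5.5, well over it.
- G = 3, SDs 3 and 1: (1 + 60)/(9 + 1) = 6.1, about twice it.
- G = 3 with repeated-measures error: (1 + 60)/1 = 61.

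The curve appears nowhere in these ratios; the unaided gap alone produces them.

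**Step 2: rejection rates by simulation** (20,000 trials per setting, curves equal, range over the four SD combinations):

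| Unaided worse by | One-way F | Repeated-measures F | Paired Variation #1 - standard |
|---|---|---|---|
| 2 dB | 32-92% | 99-100% | about 5% |
| 3 dB | 92-100% | about 100% | about 5% |

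**Step 3: the direct contrast.** The paired difference has standard error sw√2/√20, which is 0.32 dB at sw = 1 and 0.47 dB at sw = 1.5. Neither sb nor the unaided score enters it.

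**Step 4: does the unaided condition also hide a real curve effect?** Take a true 0.75 dB effect with SDs 3 and 1. The paired contrast gives 0.75/0.32 = 2.4 standard errors and about 61% power at every gap. At a 1 dB gap:

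- The one-way F rejects in about 8% of trials if Variation #1 is better, and about 0.1% if it is worse.
- The repeated-measures F on the same three conditions rejects in over 80% either way.
- Requiring a significant repeated-measures F before the paired test leaves 59-62% power.
- Requiring a significant one-way F first leaves about 6% if Variation #1 is better.
- An unpaired test of the two aided conditions, with unaided left out, has about 0.2% power. Its nominal standard error is √(2 × 10/20) = 1.0 dB.

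The loss of power therefore comes mainly from ignoring the pairing, not from including unaided.

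**Step 5: the cost of three unranked pairs.** Three unadjusted tests at 5% give a family error of up to 1 - 0.95³ = 14.3% if independent. If they are Bonferroni-adjusted instead, the difference detectable with 80% power (normal approximation, n = 20, sw = 1) rises from (1.96 + 0.84) × 0.316 = 0.89 dB to (2.39 + 0.84) × 0.316 = 1.02 dB. One named contrast avoids both.

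**The case against.** The strongest reply is that the plan has two steps and the second supplies what the first does not. Leaving out unaided gives exactly Variation #1 against standard. Unaided is a declared condition, an omnibus test followed by pairwise comparisons is a conventional sequence, and the study calls itself exploratory. The F test also answers the question its own sentence poses. All of this stands, and it limits the point.

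Three stronger readings are tempting, and the documents do not support them.

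- A reader might infer that the SRT50 analysis says nothing about the curve. That is true of the omnibus result alone; the pairwise step does address it.
- A reader might infer that the unaided condition will bury a true curve effect. Step 4 shows that this depends on an unpaired analysis, which is a separate issue, and on a rule that a non-significant F stops the comparisons. Section 2.4.3 says only that the comparisons followed the ANOVA and states no such rule.
- A reader might infer that participants without an obtainable unaided score are lost from the curve comparison. The plan mentions neither missing SRT50 scores nor complete-case deletion, and a pairwise step that drops one condition at a time need not lose them.

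The reply does not remove the lack of a ranking: the objective's own question has the same standing as two comparisons that cannot answer it.

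**Conclusion.** The point holds as a mismatch between objective and leading test, not as a missing analysis. Significance of the three-condition F cannot be read as a curve effect or, given the stated aim of equivalence, as its failure. How often it would be significant with identical curves depends on assumed SDs and on an assumed unaided gap, and at 2 dB the one-way range is wide. That its significance can come wholly from the unaided condition needs no such assumption.

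This is a secondary objective in an exploratory study, so the change is one the sponsor should make rather than one on which the trial depends. Pairing and the missing equivalence margin are neighbouring issues, but fixing either alone leaves this one open: a margin has to apply to a named contrast.

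**What to change.** In section 2.4.3:

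1. Name Variation #1 minus standard, computed from each participant's two aided SRT50 scores, as the single planned contrast for this objective, citing section 1.3 as its source.
2. Report its estimate and confidence interval whatever the ANOVA shows.
3. Report each aided-minus-unaided difference separately, as supportive evidence that the aids helped and that the test could detect a change.
4. State that neither the omnibus F nor the unaided comparisons are evidence about the curve.
5. State that a missing unaided score does not remove a participant from the planned contrast.

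The cost is a few lines of text and a re-run on scores that, from the past tense of the section, appear to be in hand; no new data are needed. Because the contrast comes from the stated objective, naming it now is not a choice made from the results, but the change should be dated as a clarification. The downside is that the unaided comparisons become supportive only.
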